1. PROJECT OVERVIEW

1.1 *Project Design*

This pilot study is an open-label randomized controlled clinical trial. It is designed to demonstrate the feasibility of utilizing emergency departments (ED) as a primary site for subject enrollment in clinical trials evaluating influenza therapeutics, providing pilot data for future clinical trial design and planning. Adults presenting to the ED with laboratory-confirmed influenza who meet Centers for Disease Control and Prevention (CDC) criteria for antiviral treatment will be enrolled. Subjects will be randomized to either oral (oseltamivir) or intravenous (IV) (peramivir) antiviral treatment.

1.2 *Objectives*

1.2.1 Efficacy

1.2.1.1 Primary Objective

To prospectively enroll high-risk subjects with laboratory-confirmed influenza into a randomized, open-label study of oral versus IV influenza therapeutic to include symptom evaluation and outcome assessments.

1.2.1.2 Secondary Objectives

Secondary Objective 1: To identify influenza-positive patients utilizing a previously established triage-based assessment and rapid testing algorithm for suspected influenza infection.

Secondary Objective 2: To retrospectively evaluate all potentially eligible patients for potential enrollment biases.

Secondary Objective 3: To create a repository of residual nasopharyngeal (NP) samples collected from ED patients with suspected influenza illness.

1.2.2 Safety

The safety will be assessed by evaluating the clinical significance of laboratory abnormalities and adverse events (AEs) and all serious adverse events (SAEs). The overall occurrences of AEs and SAEs will be reported by System Organ Class (SOC) and Preferred Term (PT). The AEs and SAEs will also be evaluated and reported by the relationship to study drug, severity and the outcome. All the results will be summarized by study arm and/or by clinical site as appropriate.

1.2.3 Pharmacokinetics

The pharmacokinetics of influenza antivirals will not be studied.

1.3 *Treatments*

All eligible subjects will be randomized to receive one of two treatment groups. They will receive either oral or IV antiviral treatment.

1.3.1 Treatment Assignment

Randomization will be carried out using a computerized randomization system in the ratio of 1:1. It will be performed by research staff after informed consent, laboratory results and verification of all eligibility criteria have been performed.

Subjects randomized to the oral treatment arm will receive oral oseltamivir. Subjects randomized to the IV treatment group will receive IV peramivir.

1.3.2 Selection and Timing of Doses

Influenza antivirals will be dosed based on creatinine clearance (CrCl) results, as described below. CrCl will be calculated using the Cockcroft Gault equation (see Manual of Operating Procedures (MOP)).

Treatment	CrCl Result	Dosage	Frequency/Duration
Oral Oseltamivir	>60 mL/min	75 mg	Twice daily (every 12 hours) for 5 days
	>30 – 60 mL/min	30 mg	Twice daily (every 12 hours) for 5 days
	>10 – 30 mL/min	30 mg	Once daily (every 24 hours) for 5 days
IV Peramivir	≥50 mL/min	600 mg	One time
	30 – 49 mL/min	200 mg	One time
	10 – 29 mL/min	100 mg	One time

1.4 *Procedures*

1.4.1 Subject Identification

Research staff will review ED adult patient charts to identify patients with a positive laboratory-confirmed influenza test during their current ED visit. If a patient appears to be eligible, research staff will approach the patient, verify that the patient meets eligibility criteria, and determine if he/she would like to participate in the study.

To be considered eligible for enrollment, a patient must meet the inclusion criteria and must not meet any of the exclusion criteria listed in the protocol at the time of screening. Screening and enrollment occur at the same visit. Screened patients who are eligible and provide written consent to participate in the study, will be randomized to a treatment arm and considered as enrolled in the study.

For secondary objective 2, research staff will identify subjects by retrospectively screening all ED records of patients who presented between November and April of the current influenza season to determine eligibility. (See Protocol).

For all eligible patients, research staff will review the ED and hospital records to retrospectively complete a set of structured clinical data forms to collect the following: basic demographic data; symptoms related to the Clinical Decision Guideline (CDG); criteria for CDC antiviral treatment; initial presentation and clinical course at the ED, including antiviral treatment, antibiotic treatment, Xpert Flu test or other influenza test information; and hospital course if subsequently admitted.

1.4.2 Randomization

Subjects will be randomized to receive one of two treatment groups using a computerized randomization system in the ratio of 1:1. Randomization will be performed at study level and not stratified by site.

1.4.3 Blinding/Unblinding

This is an open-label study, and the administration of treatments will not be blinded.

1.4.4 Replacement

No additional subjects will be recruited to replace any subjects who are lost to follow up or cannot be evaluated.

1.4.5 Data Monitoring

Data and safety will be monitored by the Safety Monitoring Committee (SMC), consisting of the IND sponsor, JHH Co-PIs, JHU Research Program Manager, Biomedical Advanced Research and Development Authority (BARDA) Medical Officer, Independent Safety Monitor (ISM), and study biostatistician (See Data and Safety Monitoring Plan (DSMP)).

2. STATISTICAL ANALYSIS CONSIDERATIONS

2.1 *Sample Size and Power*

The proposed sample size is at least 50 subjects per site, per influenza season. This sample size was determined, in collaboration with the Office of the Assistant Secretary for Preparedness and Response (ASPR)/BARDA, to be adequate for this pilot effort which is being conducted specifically to examine the feasibility of achieving higher recruitment rates than has historically been achieved in other clinical venues, and the ability to reliably collect useful therapeutic endpoint data from an ED enrollment site. Estimates are based on data from the JHH ED 2014-2015 influenza season using the CDG testing algorithm, where 1604 patients were tested for influenza between November 2014 and April 2015, and 311 influenza-positive patients were identified. Of those 311 patients, approximately 75% met CDC criteria for influenza treatment (i.e., potential enrollment in the study) and 40% were admitted to the hospital. As 2014-2015 was a robust influenza season, it is estimated that a routine influenza season would have approximately 25% fewer influenza-positive patients. Based on similar previous ED based therapeutic clinical trials conducted at the JHH ED, it is anticipated that 56% of eligible patients will agree to participate in the study. Therefore, assuming a routine influenza season, there will be an estimated 174 eligible patients, of whom 97 will be enrolled (58 discharged, 39 admitted). Based on these estimates, at least 50 (conservatively) and up to 225 subjects could be enrolled and followed for 28 days.

2.2 *Analysis Population*

The analysis population includes adults presenting to the ED with laboratory-confirmed influenza who meet CDC criteria for antiviral treatment. Detailed inclusion/ exclusion criteria are listed in the Protocol.

2.3 *Data Handling*

2.3.1 Outcome Measures and Predictors

Outcomes:

a. For the Primary Objective:

- The number of subjects successfully enrolled
- The proportion of subjects who received treatment with IV study drug in the ED
- The proportion of subjects who received (first dose) oral study drug in the ED
- The proportion of subjects who complete follow-up.

In addition, the following clinical measures will be evaluated for planning future clinical trial endpoints:

- For all study subjects:

- Reported symptoms (including FLU-PRO Symptom Questionnaire)
- Daily functional assessment
- Patient Global Impression of Change (PGIC) on Day 7 and Day 28
- Patient Global Impression of Severity (PGIS) at enrollment, and on Day 7 and Day 28
- Number of subsequent medical visits or hospitalizations within 28 days of enrollment
- Influenza-related complications including pneumonia, myocardial infarction, and stroke.

- For subjects initially admitted to the hospital from the ED:
 - Severity of disease based on Intensive Care Unit (ICU) admission, mechanical ventilation, or oxygen supplementation
 - Ordinal scale up to 14 days:
 - Death
 - Receiving mechanical ventilation or extracorporeal membrane oxygenation (ECMO)
 - In ICU (without mechanical ventilation or ECMO)
 - Non-ICU hospitalization, requiring supplemental oxygen
 - Non-ICU hospitalization, not requiring supplemental oxygen
 - Not hospitalized, but unable to resume normal activities
 - Not hospitalized with full resumption of normal activities.

b. For the Secondary Objective 1:

- The proportion of ED patients who were screened for influenza
- The proportion of screened patients who met testing criteria
- The proportion of patients who met testing criteria who were tested for influenza
- The proportion of patients tested for influenza who were positive for influenza.

c. For the Secondary Objective 2:

- The proportion of eligible patients who were enrolled
- Comparison of demographic characteristics between those who were enrolled in the study versus those who were identified to be potentially eligible through the retrospective chart review.
 - Age
 - Sex
 - Race
 - Ethnicity

d. For the Secondary Objective 3:

- The creation of a robust repository using all remnant samples of patients tested using the triage-based assessment and testing algorithm from November through April 2015 - 2017. Note that this is not a quantitative outcome.

Potential predictors (independent variables) of interest:

- Enrollment: We will compare demographic characteristics between those who were enrolled and randomized in the study versus those who were eligible but not enrolled (declined, screen failure etc.).
- Influenza Type: We will compare study outcomes between subjects with Influenza A and B.
- Other clinical characteristics: We will compare study outcomes by various subject demographic, historical (i.e. past medical history and co-morbidities), and clinical characteristics.
- Study site: There are 2 sites in the study. Study outcomes will be presented in total and by site. We will also compare subject characteristics by site for Secondary Objective 2.

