2.4.3 Descriptive Statistics of All Study Variables

Descriptive statistics including mean, median, standard deviation, range for continuous outcomes and frequency/proportion for categorical outcomes will be used to characterize study outcomes.

In addition, we will compare demographic characteristics between those who were enrolled and randomized in the study versus those who were eligible but not enrolled (declined, screen failure, etc.).

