2.2. Study Outcome Measures

Primary Objective: To prospectively enroll high-risk subjects with laboratory-confirmed influenza into a randomized, open-label study of oral versus IV influenza therapeutic to include symptom evaluation and outcome assessments.

Outcomes: The number of subjects successfully enrolled; the proportion of subjects who complete treatment with IV or oral study drug in the ED; the proportion of subjects who complete follow-up.

In addition, the following clinical measures will be evaluated for planning future clinical trial endpoints:

- For all subjects:
 - Reported symptoms (including FLU-PRO Symptom Questionnaire);
 - Daily functional assessment;
 - Patient Global Impression of Change (PGIC) on Day 7 and Day 28;
 - Patient Global Impression of Severity (PGIS) at enrollment, and on Day 7 and Day 28;
 - Number of subsequent medical visits or hospitalizations within 28 days of enrollment; and
 - Influenza-related complications including pneumonia, myocardial infarction, and stroke.
- For subjects initially admitted to the hospital from the ED:
 - Severity of disease based on Intensive Care Unit (ICU) admission, mechanical ventilation, or oxygen supplementation; and
 - Ordinal scale up to 14 days:
 - Death;
 - Receiving mechanical ventilation or extracorporeal membrane oxygenation (ECMO);
 - In ICU (without mechanical ventilation or ECMO);
 - Non-ICU hospitalization, requiring supplemental oxygen;
 - Non-ICU hospitalization, not requiring supplemental oxygen;
 - Not hospitalized, but unable to resume normal activities; and
 - Not hospitalized with full resumption of normal activities.

Secondary Objective 1: To identify influenza-positive patients utilizing a previously established triage-based assessment and rapid testing algorithm for suspected influenza infection.

Outcomes: The proportion of ED patients who were screened for influenza; the proportion of screened patients who met testing criteria; the proportion of patients who met testing criteria who were tested for influenza; the proportion of patients tested for influenza who were positive for influenza.

Secondary Objective 2: To retrospectively evaluate all potentially eligible patients for potential enrollment biases.

Outcome: The proportion of eligible patients who were enrolled; comparison of demographic characteristics between those who were prospectively enrolled versus not enrolled.

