4.1. Retrospective Chart Review

In order to evaluate the full potential ED population who might have met criteria for enrollment, all potentially eligible patients will be evaluated via a retrospective chart review. Basic demographic characteristics of patients who were not approached for enrollment, and those who were approached but not enrolled, will be compared (in a de-identified manner) with those who were enrolled into the Randomized Controlled Trial of Influenza Antivirals.

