4.1.2. Eligibility Criteria

Inclusion Criteria

Full ED chart review will be performed on individuals who meet the following inclusion criteria at the time of the ED visit:

- 1) 18 years of age or older;
- 2) Adult ED visit between November and April of each influenza season, or later, at the Co-PIs' discretion, based on influenza prevalence; and
- 3) Positive influenza test associated with the ED visit

Exclusion Criteria

There are no exclusion criteria.

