4.2.2. Screening

Eligible subjects will be recruited by dedicated research staff 24 hours a day, 7 days a week. Screening and enrollment occur at the same visit.

Under a HIPAA waiver of consent, research staff will review current ED patient charts for adult ED patients who have a positive laboratory-confirmed influenza test during their current ED visit. If a patient appears to be eligible, the research staff will approach the patient's ED provider to inform them that the patient is potentially eligible. Alternatively, providers may also refer potentially eligible patients to research staff. With the provider's approval, research staff will approach the patient, verify that the patient meets eligibility criteria, and determine if he/she would like to participate in the study.

Eligibility information will be recorded for every patient who is approached for potential study enrollment using a Screening and Enrollment Log. Patients who do not meet inclusion criteria or who meet an exclusion criterion will be deemed ineligible; the reason for their exclusion will be recorded. Screened patients who meet all inclusion and no exclusion criteria, i.e., who are eligible, will be approached for informed consent. For those patients who decline participation, the given reason for refusal to participate will be recorded. Screened patients who are eligible and provide written consent to participate in the study, will be randomized to a treatment arm and considered as enrolled in the study.

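### The enrollment-bias comparator (Secondary Objective 2) counts screen failures as eligible and is worded differently across the documents; the likely effect is small, but one definition is needed

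*Combined protocol and SAP*

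**What the plan says.** The comparator for enrolled subjects is described in several ways.

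- SAP 2.3.1, predictors list (Enrollment): "versus those who were eligible but not enrolled (declined, screen failure etc".). SAP 2.4.3 has the same: "versus those who were eligible but not enrolled (declined, screen failure, etc".).
- SAP 2.3.1(c), outcomes for Secondary Objective 2: "versus those who were identified to be potentially eligible through the retrospective chart review". It does not say whether enrolled subjects are removed.
- Protocol 2.2: "comparison of demographic characteristics between those who were prospectively enrolled versus not enrolled", with no mention of eligibility.
- Protocol 4.1: "Basic demographic characteristics of patients who were not approached for enrollment, and those who were approached but not enrolled, will be compared" with the enrolled.
- Protocol 4.1.2 admits to the chart review any adult with an ED visit in season and a positive influenza test, and adds: "There are no exclusion criteria".

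Two places define eligibility for the trial. SAP 1.4.1 says an eligible patient "must meet the inclusion criteria and must not meet any of the exclusion criteria listed in the protocol at the time of screening". Protocol 4.2.2 says: "Patients who do not meet inclusion criteria or who meet an exclusion criterion will be deemed ineligible".

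The comparison covers age, sex, race and ethnicity (SAP 2.3.1(c)). The other outcome of this objective is the proportion of eligible patients enrolled. SAP 3.3 states that the analysis is outside the SAP's scope. Protocol 9.3 names a t-test or chi-squared test for it, while SAP 2.4.2 says the study has no hypothesis testing.

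**The concern.** The objective is to find out whether recruitment was selective among patients who could have been enrolled. A patient who failed screening could not have been randomized, so the comparator in SAP 2.3.1 and 2.4.3 includes people whom the documents elsewhere call ineligible. Because the wording varies and no analysis section settles it, two analysts could each follow the text and use different comparators and different denominators.

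This matters for the variables being compared. Age 65 or older and American Indian/Alaska Native are among the CDC criteria in Protocol 4.2.1, so every patient who meets no CDC criterion is under 65 and is not American Indian or Alaska Native. Putting such patients in the comparator creates an age gap, and possibly a race gap, even when recruitment was not selective.

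**Working it through.** **1. The plan's funnel (SAP 2.1, Protocol 9.2), one routine season at one site.**
- Positives: 311 × 0.75 = 233.
- Meeting CDC criteria: 233 × 0.75 = 174.9 (plan: 174).
- Enrolled: 174 × 0.56 = 97.4 (plan: 97).

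The plan's figures reproduce.

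**2. Size of the set under two readings.**

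| Reading | Comparator | Meeting no CDC criterion | Proportion enrolled |
|---|---|---|---|
| Meeting CDC criteria | 174 − 97 = 77 | 0 | 97/174 = 56% |
| All influenza-positive | 233 − 97 = 136 | 233 − 174 = 59 (43%) | 97/233 = 42% |

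The 174 is not reduced for the 4-day symptom limit or the trial exclusions, so it overstates the trial-eligible number.

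**3. Age gap with no recruitment selection, all positives used.** Let q be the share of positives aged 65 or older (assumed 10%, 20% or 30%; the documents give none), with the 97 enrolled at random from the 174.
- Share 65+ among the enrolled: p = 233q/174.
- Share 65+ in the comparator of 136: p × 77/136.
- q = 10%: 13.4% against 7.6%, a gap of 5.8 points.
- q = 20%: 26.8% against 15.2%, a gap of 11.6 points.
- q = 30%: 40.2% against 22.7%, a gap of 17.4 points.

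In simulation (400,000 runs; number aged 65+ binomial on 233, enrollment a random draw, uncorrected chi-square at an assumed 5% level), this comparator flags a difference in 34%, 59% and 83% of site-seasons. The comparator of 77 flags about 5%.

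**4. Screen-failure wording alone.** Add s screen failures to the 77. A fraction f of them lack a CDC criterion, and the rest have the same 65+ share as the 174. The expected gap is p × fs/(77 + s). For q = 20%, s = 40, f = 0.25: 26.8 × 10/117 = 2.3 points. The same simulation gives these false-flag rates over s = 10 to 40 and the three values of q:
- f = 0.25 or less: about 5-8%.
- f = 0.5: about 5-17%.
- f = 1: about 6-58%, the top value needing 40 failures and q = 30%.

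The late failures named in Protocol 5.1.1 (low creatinine clearance or hemodialysis, a positive pregnancy test, missing laboratory studies) need not lack a CDC criterion, so a small f is plausible.

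**5. Sensitivity of step 3.** If trial exclusions remove a further 10-30% of the 174, and excluded patients are from twice to half as likely to be 65 or older (both assumed), the rate for the all-positives comparator runs from about 6% to 95%. The illustration gives a direction and a mechanism, not an estimate.

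**The case against.** The strongest reply is that the documents, read for their purpose, already point to a trial-eligible set. The objective speaks of potentially eligible patients, and Protocol 4.1 opens by saying the review concerns the population who might have met enrollment criteria. SAP 1.4.1 and Protocol 4.1.1 and 4.1.3 refer to determining or confirming eligibility. Protocol 4.1.2 can be read as saying only whose charts are reviewed in full. This stands: the all-positives reading is the less natural one. It does not remove the explicit inclusion of screen failures among the eligible, nor does it give an analyst one governing definition. Protocol 4.1.1 also removes only patients who fail inclusion criteria, which fits the broad list in 4.1.2.

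A reader might infer three stronger claims, which the documents do not support.
- That age or race differences could never be separated from the entry criteria. Protocol 4.1.4 abstracts the CDC criteria and Protocol 4.1.1 logs eligibility information, so a filter can largely separate them.
- That the 34-83% rates follow from the screen-failure wording. They belong to the all-positives comparator only.
- That the plan compares the enrolled with a group containing them, shrinking a true difference to 77/174 = 44% of its size. This rests on SAP 2.3.1(c) alone; the other descriptions give a non-enrolled group, and comparing enrollees with their source population is a legitimate summary.

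It is also fair to say that the objective is secondary in a mainly descriptive pilot, and that the false-flag rates presuppose the test in Protocol 9.3.

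**Conclusion.** The contradiction in SAP 2.3.1 and 2.4.3 is real, and the comparator for Secondary Objective 2 is not defined consistently. The wording lets ineligible patients enter the comparison but does not require the broadest reading. The screen-failure wording alone probably has a small effect: about 5-8% against a nominal 5%, if a quarter or fewer of the failures lack a CDC criterion. The effect is large only if all non-enrolled positives are used, where 59 of 136 (43%) meet no CDC criterion and the proportion enrolled falls from 56% to 42%. These figures rest on the planning funnel, random enrollment, assumed age shares and an assumed 5% level; the size in the trial's own data is unknown. The primary feasibility counts and the arm summaries are unaffected. Severity: minor.

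**What to change.** - Delete screen failure from the eligible comparator in SAP 2.3.1 and 2.4.3.
- Because SAP 3.3 places the analysis outside the SAP, define one set in the Protocol (2.2 and 4.1) and have the SAP refer to it: influenza-positive patients who meet the trial inclusion criteria and no trial exclusion criterion ascertainable from the chart.
- Use this set as the denominator for the proportion enrolled and, with enrolled subjects removed, as the comparator.
- Report the non-enrolled in three strata: not approached; approached and declined; approached and found ineligible only on a criterion learned at the bedside (for example, G6PD deficiency by patient report). Keep the third out of the main comparison, or show results with and without it. State that bedside-only criteria cannot be applied to patients who were not approached.
- Report chart-ascertainable screen failures separately, with reasons.
- Check that symptom onset and the chart-ascertainable exclusions are captured for every patient in the set.

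The cost is a wording change, an analysis filter and at most a few added data items. The downside is a smaller comparator, with some criteria applied only in part.
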